Session 2:	Target training to facilitate walking; Come	Targeting with and without cat's harness/leash
Session 3:	Practice walking in harness/leash; Watch me	Work on watch me, come & practice walking
Session 4:	Practice walking in harness/leash; Sit	Work on training sit; practice walking
Session 5:	Practice walking in harness/leash; Go to mat	Work on go to mat; practice walking
Session 6:	Training challenge: Walk a course, stop and perform learned behaviors along path	Work on behaviors; practice walking; schedule 6-week assessment

Approach and Assessments:

Specific survey and behavioral assessments for each specific aim are outlined below. During assessments children and a parent/adult household member will complete several short, validated questionnaires. There are adaptable procedures, allowing for flexibility in administration. Participants can fill out the questionnaire on their own or an assessor can read aloud and allow the participant to respond. Scoring will conform to standard methods specified for each assessment. Cat-specific questionnaires have been adapted from previously validated animal questionnaires. All child and cat assessments will occur at each of the three assessment time points (Baseline, six weeks and 1 year). In total, assessments will include 4 pages of survey questions to be completed by the child, one 11-page

survey about the cat's behavior to be completed by a parent/adult in the household, and 8 minutes of behavioral testing by the cat and child during each assessment. Cat's will also participate in one additional behavioral attachment test with the primary adult caretaker during the initial assessment for initial paired comparison with child-cat bonds.

Aim 1: To evaluate the nature and quality of bonds shared between cats and children with DD.

Our hypothesis is that cats and children will show evidence of bonds prior to intervention. However, the quality and type of relationships shared between cats and children are predicted to be variable and less secure than cat-adult bonds initially. *Note: *The successful completion of Aims 2 & 3 is not dependent on the presence of secure attachment bonds between children and cats prior to AAI participation.* We expect CAT participation to improve attachment scores by week 6 (Aim 3), similar to what we have observed in our dog AAI research [6].

Aim 1 Assessments:

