1. Behavioral Attachment Test: A cat sociability [11] and Secure Base attachment test [25] will be conducted to evaluate the cat-child bond (and the cat-adult bond at baseline). The cat's contact, proximity seeking, gaze, exploration, play and avoidance behavior will be evaluated over a series of 2-minute sessions (8 minutes total) where the child (or parent) is either present and passive, present and attentive, absent or reuniting with the cat. Behaviors will be double coded from video (to assess inter-rater reliability), coders will be blind to group assignment. Attachment style classifications will be made in line with previously validated methods [7].

2. Child-Cat Relationship Surveys: Children will complete a 1-page Children's Treatment of Animals Questionnaire (CTAQ) [28], 1-page Pet Care Responsibility Inventory [29], and a 1-page Lexington Attachment to Pets Scale (LAPS) [30]. These will characterize initial child-cat attachment (Aim 1) and to evaluate AAI outcomes related to predicted strengthening of the child-cat bond at 6-week and 1-year assessments (Aim 3).

Aim 2: To develop & evaluate the efficacy of a novel Cat Assisted Training (CAT) intervention aimed at increasing physical activity in early adolescents with developmental disabilities.

Our hypothesis is that participation in this novel CAT intervention will result in high participant retention and significant improvement in study related physical activity goals when compared with baseline measures, and when compared with a randomized control group.

Aim 2 Assessments:

1. Evaluation of CAT intervention retention: Our retention goal for this program is 68% (overall) - 76% (experimental group), as this is what we achieved in our prior dog walking/training AAI [NIH R21HD091895]. Lower retention would not rule out future CAT interventions but would signal that improvements may be needed to increase effectiveness. If attrition occurs, we will evaluate retention

across the course of the six-week CAT intervention using a survival curve to help identify any elements that could have contributed.

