2. Evaluation of CAT intervention for increasing joint physical activity: As in our prior research evaluating dog training AAls, survey items about pet walking, training and joint activity found on the validated Pet Care Responsibility Inventory [29] will be used to determine if intervention participation predicts a subsequent increase in joint physical activity (including walking and training behaviors) in CAT participants after the intervention, when compared with baseline measures and the control group. At each training session participants will also be asked if they completed their training and walking homework in the prior week, providing information about engagement that can be used to guide future development of the CAT program. This information will guide the development of our final program for our R01 proposal, where we will conduct a larger scale study of the CAT program, collecting additional physical activity data using accelerometers.

3. Evaluation of cat training success: We will evaluate the training success of cats across the behaviors presented in Table 1, primarily to help inform (and modify, if needed) future training strategies and goals. We have found in past studies that the number of behaviors an animal learns during the intervention itself is less important to AAI health-related outcomes than the process of engaging in the intervention [6], nonetheless we aim to make the AAI training goals and methods as successful and data driven as possible. We will also evaluate behavior changes across assessment time points using the validated 11 page Feline Behavioral Assessment & Research Questionnaire (Fe-BARQ) [31] completed by a parent/adult in the household.

Aim 3: To evaluate the impact of a CAT intervention on social wellbeing & the child-cat bond.

Our hypothesis is that participation in a novel CAT intervention will result in increased feelings of social wellbeing, increased attachment towards the family cat and will promote greater independent responsibility for the family cat by adolescent participants with DD when compared to baseline measures, and controls. We also predict that we will find behavioral evidence of increased sociability and higher rates of secure attachment among cat-child dyads following intervention when compared to baseline.

Aim 3 Assessments:

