To assess efficacy of the CAT intervention we planned to conduct a survival analysis for program retention and for the population of cats reaching each milestone in the training program (Aim 2). However, our retention rate was high at 97% so no survival analysis was necessary. Cat milestones were analyzed as part of our fidelity analysis using non-parametric correlation tests appropriate for non-normal and/or non-continuous data (e.g., Spearman's Rank Correlation). To assess the effectiveness of CAT (Aims 2 & 3), we will perform paired t-tests, independent t-tests, linear regression and analysis of variance as appropriate to evaluate any changes in physical activity/joint walking, sociability (cat) and social wellbeing (child) scores, and HAI measures, for CAT participants across three assessment time points. We will also compare any improvement in the training group to changes within the control group. This study design allows us to evaluate the difference between the CAT intervention group and control group after accounting for baseline variability among child-cat pairs (see below). The incorporation of baseline data will reduce the noise level in our model and therefore enhance the statistical efficiency. For any data not conforming to the requirements of parametric tests (e.g., normality), we will use non-parametric tests such as McNemar's Test, Fisher's Exact test, etc.). A fully randomized control trial approach will be utilized. Block randomization will be conducted to ensure a balance in the sample size between groups

Modification Requested:

“After consultation and approval from our funder (NIH program officer), we propose to expand the participant age range in our study from 10-12 years to 8-17 years. This adjustment aligns with our original intention to explore the intervention efficacy in children with disabilities more broadly. We have successfully run AAI programs with 8–17-year-old children previously. The revision maintains our current procedures and assessments, ensuring no additional risk to our participants.”

HE-2022-29 - Modification

Date: September 13, 2023

PI: [name]

Department: ASC - Animal & Rangeland Sciences, HHS - Public Health/Human Sci Admin

Re: Modification - HE-2022-29

The development and evaluation of a novel Cat Assisted Training (CAT) intervention for youth with developmental disabilities and their family cat.

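### The Aim 3 behavioural prediction is judged against a baseline visit that includes an extra cat test; the CAT-versus-control contrast, which this cannot bias, should carry the conclusion

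*Combined protocol and SAP*

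**What the plan says.** The Approach and Assessments section sets the schedule: "All child and cat assessments will occur at each of the three assessment time points (Baseline, six weeks and 1 year"). The child's share is "8 minutes of behavioral testing by the cat and child during each assessment". One element belongs to the first visit alone: "Cat's will also participate in one additional behavioral attachment test with the primary adult caretaker during the initial assessment". Its stated purpose is "for initial paired comparison with child-cat bonds", which is an Aim 1 question.

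Item 1 of Aim 1 Assessments agrees. The test "will be conducted to evaluate the cat-child bond (and the cat-adult bond at baseline"). The same item gives one format for both partners, "over a series of 2-minute sessions (8 minutes total) where the child (or parent) is either present and passive", followed by attentive, absence and reunion phases.

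The Aim 3 hypothesis has two sentences. The first covers the child's social wellbeing, attachment and responsibility, and names both baseline and controls as comparators. The second covers cat behaviour. It predicts more sociability and "higher rates of secure attachment among cat-child dyads following intervention when compared to baseline", and does not name controls.

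The post-data-collection update to the statistical analysis plan lists paired t-tests among the methods for assessing change "for CAT participants across three assessment time points", and gives McNemar's test as one of the non-parametric alternatives.

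**The concern.** The baseline and follow-up child tests are compared as if taken under like conditions. At baseline a cat may already have been through a separation and reunion with the adult before it is tested with the child. At six weeks and one year the plan gives it no such earlier test. If an earlier test changes proximity seeking, contact or the attachment classification, through fatigue, stress or habituation, then dropping it at follow-up moves the child-test result with no help from the intervention.

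What is at stake is one stated conclusion: that cat sociability and secure attachment with the child rise after CAT. Read as change from baseline within the CAT arm, that conclusion cannot separate an intervention effect from a change in testing conditions. The error could run either way, producing a gain or hiding one.

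**Working it through.** **1. Test load per visit** (Approach and Assessments; Aim 1 Assessments, item 1).

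| Visit | Child test | Adult test | Total |
|---|---|---|---|
| Baseline | 8 min | 8 min | 16 min |
| Six weeks | 8 min | none | 8 min |
| One year | 8 min | none | 8 min |

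The Control Group section gives controls the same three assessments, so the table applies to both arms. Controls are offered classes only after the third assessment, so they remain an untrained comparison at one year too.

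**2. What each contrast estimates.** Let τ be the intervention effect on a child-test score. Let s be the shift from baseline to follow-up caused by the change in test load, together with repeat testing and the passage of time.

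- Within CAT, before-after: expected change = τ + s.
- CAT change minus control change: (τ + s) − s = τ.

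For the secure/insecure classification the argument does not depend on the scale. With no intervention effect, randomisation and a shared schedule give both arms the same distribution at every visit, so a between-arm test keeps its level. This holds unless test load acts differently in the two arms, and nothing in the documents suggests that it does.

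**3. Which contrast the prediction uses.** The Aim 3 behavioural sentence names baseline only, so it maps to τ + s.

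**4. Illustration on assumptions only.** The documents give no value for s. Assume normal change scores, 25 dyads per arm as planned, no true effect (τ = 0), two-sided α = 0.05, and s expressed in SDs of the change score. Simulation with 40,000 replicates gave these false-positive rates:

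| Assumed s | Paired t within CAT | Between-arm t on change |
|---|---|---|
| 0 | 5% | 5% |
| 0.2 | 16% | 5% |
| 0.3 | 30% | 5% |
| 0.5 | 67% | 5% |

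The last column is the useful one: it does not move. The middle column shows only how the paired test responds to a shift of each size. It is not an estimate for this trial.

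**5. Price of the between-arm contrast.** Let ρ be the baseline-to-follow-up correlation, n the number per arm and σ² the variance at each visit. In large samples:

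- Variance of the paired mean change: 2(1 − ρ)σ²/n.
- Variance of the baseline-adjusted difference between arms: 2(1 − ρ²)σ²/n.
- Ratio of standard errors: √(1 + ρ).

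This is 1.00 at ρ = 0, 1.22 at ρ = 0.5, and approaches 1.41 as ρ approaches 1. The documents do not give ρ, so 0 to 1 is the range.

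**The case against.** The strongest reply is that the planned analyses already contain the cure. Aim 3 Assessments, item 1, compares child-cat bonds between the arms at six weeks and one year. The statistical update says that improvement in the training group will be set against change in controls, after accounting for baseline variability, and its outcome list includes cat sociability. On that reading, the absence of controls is a gap in one sentence of the hypothesis and not in the analysis. This largely stands. It is why the randomised comparison is not in question. But the between-arm tests sit beside the paired tests, and nothing says which of them decides the behavioural prediction, whose own wording points to the paired ones.

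A second reply is that no carry-over has been shown. If the child test came first, or the two tests were well separated, the adult test need not have affected the baseline child test. This also stands. The available text is silent on order, spacing and counterbalancing. Parts of the document were withheld, and the test methods are cited to outside papers, so the answer may lie elsewhere.

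A third is that repeat testing weakens any uncontrolled before-after comparison, with or without an adult test. That is true, and the remedy is the same.

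**Conclusion.** The point holds in a limited form. It is documented that cats take two tests at baseline and one at each follow-up, and that the behavioural prediction is worded against baseline only. It follows that a within-CAT change in attachment or sociability would absorb any shift from test load or repeat testing. The size and direction of that shift are unknown.

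A reader might infer three stronger things that the documents do not support:

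- That the conditions of the child test do change between visits. Order and spacing are not given, so they only may change.
- That the efficacy comparison is biased. Both arms share the schedule and between-arm comparisons are planned, so a common shift cancels.
- That the trial carries a particular inflated error rate. Every such figure rests on an assumed shift, including the 16% to 67% shown above.

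**What to change.** - Restate the Aim 3 behavioural prediction as CAT versus control.
- Base the Aim 3 attachment and sociability conclusion on the between-arm contrast at six weeks and one year, adjusted for the baseline child-test result.
- Label within-CAT change on these measures as descriptive.
- Report the order and spacing of the two baseline tests if video or session records allow. If order varied, a before-after result restricted to dyads whose child test came first may be shown as a sensitivity check. If order did not vary, that check is empty or changes nothing. The between-arm contrast does not need it, nor a test-order covariate.

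The cost is a few sentences of plan wording and a look at existing recordings, with no new visit or procedure. Because the update was written after data collection, the change of emphasis should be dated and its reason given. The statistical downside is a somewhat wider interval than the paired test gives, by the factor √(1 + ρ) derived above.

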Oregon State University over a two-year period. 100 kitten-owner pairs enrolled in the program during this time, with 50 assigned to the training class (experimental group); 86% of owners completed the 6-week program. Owners that completed the course attended 91% of the class sessions and 84% of them participated in research testing at baseline and follow-up. Cats also readily learned behaviors through use of positive reinforcement training. Successfully learned behaviors included “go to mat and stay”, “sit”, “stand”, “target”, “walk on harness with leash” and more advanced behaviors such as “stay” while in a kayak. Drs. [name] & [name] have also offered multiple highly successful summer cat training camps where local youth were taught to train shelter/foster cats.

Cats share many traits that have predicted AAI success in other species: Prior research suggests that the quality of attachment between human and animal AAI participants is an important predictor of health outcomes and AAI success [6], [18]. Members of our research team have evaluated cat-owner attachment bonds by exploring if cats can be categorized into the same secure and insecure attachment styles in a strange situation as seen in humans [24] and domestic dogs [25]. Drs. [name] and [name] have found that like human infants and pet dogs, kittens ($n = 70$) and adult cats ($n = 38$) can display either secure or insecure attachment styles toward their adult owner, with the majority (64 - 69%) displaying a secure attachment (similar to the dog and human literature). What we have found in our work looking at dog-child attachment, is that often stable caregiver attachment relationships have not yet been established between children and their dogs prior to intervention, and that intervention participation significantly increases secure attachment formation between children and their animal partners [25]. We plan to evaluate this in cats.

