50 early adolescents with a DD, between the ages of 8-17 years whose family includes at least one cat at the time of enrollment (see Sample Size Justification & Data Analysis) will be recruited from Corvallis OR and the surrounding communities through schools, community-based programs serving children with developmental disabilities (DDs) and through social media). A DD will be confirmed through parent report (e.g., initial recruitment conversations, and documented through demographic questionnaire). Although developmentally appropriate and adapted pedagogical techniques will be implemented within all intervention protocols, inclusion criteria for child and cat safety require all participants to follow basic instructions. To assess this, participants will complete the Head-Toes-Knees-Shoulders task (HTKS) [27]. This task requires participants to follow basic and more complicated instructions, including rule changes. To participate a minimum score of 1 (range 0-2) on 90% of the test items will be required of participants. For safety cats showing signs of aggression towards humans will not be eligible to participate. Cats will be carefully monitored to ensure their welfare during all activities. Because restricting the age of cats could limit human participant eligibility, and because there is evidence that a cat's age is not a reliable predictor of training success [10], for the proposed study we will allow any cat over 8 weeks to participate as long as they meet the above criteria, and will collect data on age as a variable. In recent years, we have successfully taken this approach with our dog training AAls. Dyads meeting eligibility requirements will be randomly assigned (Randomized Control Trial) to either the CAT intervention (n=25) or Control (n=25) group after completing the consent/assent process. Dyads assigned to the control group will have the opportunity to participate in training classes after study participation is complete to ensure equal access to a potentially beneficial AAI. Each class will last 45-min for 6 sessions (see Table 1).

Study Groups: There will be 3 assessments per participating dyad over the course of 1 year; after initial enrollment (baseline), after six weeks (post-intervention or time matched control) and 1-year after enrollment. All participants (experimental & control groups) will complete each of these assessments.

CAT intervention Group

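### Attrition is examined only within the six-week CAT course, and that analysis was dropped on an undefined 97%; control-arm loss and loss between six weeks and 1 year go unexamined, with no missing-data method

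*Combined protocol and SAP*

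**What the plan says.** Aim 2 Assessments, item 1, sets the benchmark: "Our retention goal for this program is 68% (overall) - 76% (experimental group), as this is what we achieved in our prior dog walking/training AAI". It then plans one analysis: "If attrition occurs, we will evaluate retention". The scope and method given for that analysis are limited to CAT participants on the course, by survival curve.

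The update to the statistical analysis plan, which is headed as written after data collection, withdraws it: "However, our retention rate was high at 97% so no survival analysis was necessary". The sentence before speaks of retention in the programme and of cats reaching training milestones.

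For efficacy the same update says "we will perform paired t-tests, independent t-tests, linear regression and analysis of variance as appropriate". McNemar's and Fisher's tests are the fallbacks, and the arm difference is to allow for baseline.

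On design, dyads are "randomly assigned (Randomized Control Trial) to either the CAT intervention (n=25) or Control (n=25) group". Both arms are assessed at baseline, six weeks and 1 year (Study Groups), and Aim 3 compares child-cat bonds between arms at the two later visits. The sample size section recruits 25 per group, against a computed 10 to 15, to absorb attrition.

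The document names no analysis population, missing-data method, attrition comparison by arm or sensitivity analysis.

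**The concern.** Controls do not take the course, so a curve over the course says nothing about them. The course also ends about 46 weeks (52 - 6) before the last visit. Yet the aim of lasting responsibility rests on that visit, and the arms may have different reasons to leave or stay: controls are offered the classes only after the third assessment, while CAT families have already had them.

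Finishing a course is also not the same as supplying outcome data. Of the team's own public cat classes, the Preliminary Data section says: "Owners that completed the course attended 91% of the class sessions and 84% of them participated in research testing at baseline and follow-up".

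If leavers differ from stayers, an analysis of stayers can misstate the arm contrast. Recruiting extra dyads protects power but does nothing about that bias.

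**Working it through.** **1. The plan's own power figures.** The effect size, SD, alpha and test are not stated. I assume a two-sample t-test, two-sided at 0.05, solve for the standardised effect at 10 per group, and predict power at 15.

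| Outcome | Stated at 10 | Solved effect | Predicted at 15 | Stated at 15 | At 19 v 15 |
|---|---|---|---|---|---|
| Care and responsibility | 92% | 1.59 | 98.8% | 99% | 99.4% |
| Animal walking | 79% | 1.31 | 93.3% | 93% | 95.7% |

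The stated figures agree with each other. One-sided, the last column is 99.1% and 94.3%. Outcomes without a power statement lose more between 25 v 25 and 19 v 15: from 79% to 61% for an effect of 0.8 SD, and from 41% to 29% for 0.5 SD.

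**2. Where loss can occur and where it is examined.**

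| | Baseline to six weeks | Six weeks to 1 year |
|---|---|---|
| CAT | Survival curve planned, then dropped | Nothing planned |
| Control | Nothing planned | Nothing planned |

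**3. What the 97% could count.** 24/25 = 96%, 48/50 = 96% and 49/50 = 98%, so it is not a whole count out of 25 or 50. Counts such as 29/30, 58/60 (both 96.7%) or 97/100 fit. An IRB modification raises target enrolment from 60 to 100 participants but does not relate this to the 50 dyads. The text does not settle the denominator, arm or visit.

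**4. What each listed test does with a dyad seen at six weeks but missing 1 year.**
- Classical ANOVA over three visits: discards the dyad, including its six-week score.
- Paired t-test or McNemar's test: drops the dyad from any pair that includes 1 year, but keeps it for baseline to six weeks.
- Independent t-test or regression at a single visit: keeps it at six weeks and loses it at 1 year.

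All of them take those analysed to stand for those lost.

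**5. Planning retention.** With equal arms in the dog study (assumed), control retention is 2 x 68% - 76% = 60%. In this trial that gives 25 x 0.76 = 19 CAT and 25 x 0.60 = 15 control dyads, or 34 of 50 (68%). The visit to which the dog-study rates refer is not stated. In the cat classes, 0.86 x 0.84 = 72% of owners both finished and had baseline and follow-up testing.

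**6. Bias.** In one arm, the stayers' mean minus the mean of all randomised dyads is (share lost) x D, where D is the stayer-minus-leaver difference. D is assumed to be 0.5 to 1.0 SD. The bias in the contrast is the CAT value minus the control value.

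| Who differs | 76% CAT, 60% control | 97% in both arms |
|---|---|---|
| Only CAT leavers do worse | 0.24D = +0.12 to +0.24 | 0.03D = +0.015 to +0.03 |
| Leavers do worse in both arms | (0.24 - 0.40)D = -0.08 to -0.16 | 0 |
| CAT leavers worse, control leavers better | (0.24 + 0.40)D = +0.32 to +0.64 | 0.06D = +0.03 to +0.06 |

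**The case against.** The only retention figure observed in this trial is 97%. If it covers both arms to 1 year, the bias is negligible. The 76% and 60% come from a dog study, and the 60% is inferred. An overall retention goal is set, so controls are not wholly ignored, and the deferred classes give them a reason to stay. The 84% comes from public kitten classes with follow-up timing unstated. All of this stands, and it makes the size of the problem conditional. It does not remove the gap: a goal is not an analysis, and an undefined percentage cannot show completeness at 1 year.

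A reader might infer more than the documents support:
- **That every listed test drops a dyad with any missing visit.** Single-visit tests and the baseline to six-week pair keep a dyad that misses only 1 year.
- **That six-week precision falls by about a fifth.** The figure would be sqrt((1/19 + 1/15)/(2/25)) = 1.22 for the standard error. It needs a three-visit ANOVA, which the plan does not commit to, together with dog-study losses all falling after six weeks.
- **That the trial loses power.** The two powered outcomes stay at about 94% or more at 19 v 15. Only outcomes without a power statement are exposed.
- **That attrition flatters CAT.** If leavers do worse in both arms at the planning rates, the contrast is understated.
- **That the 97% means course completion only.** Its context suggests so, but the text does not say it.

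**Conclusion.** The concern holds in a limited form. It is certain that loss in the control arm and loss after six weeks have no planned examination, that the one planned analysis was dropped on a figure without arm, visit or denominator, and that no missing-data method is named. Whether this biases the results is conditional. Near 97% retention in both arms at 1 year, the bias is about 0.015 to 0.03 SD and at most 0.06. At the planning rates it could run either way: -0.08 to -0.16 SD if leavers do worse in both arms, and +0.12 to +0.24 SD if only CAT leavers do. These sizes rest on an assumed leaver-stayer difference of 0.5 to 1.0 SD, equal arms in the dog study, and its rates applying at 1 year. The issue is possible bias in the 1-year comparison, not power for the two powered outcomes.

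**What to change.** 1. Define the 97%: what is counted, in which arm or arms, up to which visit, and out of how many.
2. Report completed assessments by arm at baseline, six weeks and 1 year over all randomised dyads, and compare the baselines of leavers and stayers.
3. For continuous outcomes, replace the paired t-tests and ANOVA with one longitudinal mixed model that takes the baseline, six-week and 1-year scores all as outcomes. Use a common baseline mean for the arms, visit, arm by visit, and within-dyad correlation. Every randomised dyad with any score then contributes, including one with baseline only, and the arm contrast is estimated at six weeks and at 1 year.
4. That model relies on loss being explained by observed scores. If 1-year loss is not trivial, add a simple sensitivity analysis in which leavers' unseen outcomes are shifted by a range of amounts, separately by arm.
5. Label all of this post hoc, because the update was itself written after data collection.

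The cost is revised SAP wording and slightly more analysis work, with no new data. The reported retention may look less favourable than 97%.

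### No baseline-adjusted CAT-versus-control comparison is named as the test of efficacy, so before-after tests inside the CAT arm can stand as evidence of effect

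*Combined protocol and SAP*

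**What the plan says.** All references are to the Combined protocol and SAP.

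- **Sample Size Justification and Statistical Analysis Plan, post-data-collection updates.** For the effectiveness of CAT, "we will perform paired t-tests, independent t-tests, linear regression and analysis of variance as appropriate", and the changes to be evaluated are those "for CAT participants across three assessment time points". The control arm comes in the next sentence: "We will also compare any improvement in the training group to changes within the control group". The design is then said to be one that "allows us to evaluate the difference between the CAT intervention group and control group after accounting for baseline variability among child-cat pairs", with the reason that "The incorporation of baseline data will reduce the noise level in our model and therefore enhance the statistical efficiency". The rest of that paragraph names no model, primary outcome or deciding time point. The non-parametric fallbacks named are McNemar's test, which is paired, and Fisher's exact test, which can compare arms but does not adjust for baseline.
- **Aim 2.** The hypothesis is framed both ways: "when compared with baseline measures, and when compared with a randomized control group". The item on joint physical activity does the same: "when compared with baseline measures and the control group".
- **Aim 3 hypothesis.** Child wellbeing, attachment and responsibility are set against both baseline and controls. The behavioural prediction that follows, on sociability and attachment style, is not. It expects "higher rates of secure attachment among cat-child dyads following intervention when compared to baseline" and does not mention controls.
- **Aim 3 Assessments.** Item 1 plans to compare child-cat bonds between arms at both follow-up visits, using the attachment test and the surveys. Item 3 plans a between-arm comparison of responsibility scores. Item 2 describes the sociability test as taken before and after the programme and does not explicitly name controls.

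**The concern.** A paired test in one arm asks whether scores changed. It does not ask whether CAT changed them. The design gives several reasons for change without any intervention. Cats are eligible from 8 weeks of age, so the youngest could be about 60 weeks old (8 + 52) at the last visit. The children age a year. The same 8-minute behavioural test and the same surveys are given at three visits.

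Randomised controls assessed on the same schedule remove all of this, but only if the between-arm contrast carries the conclusion. As written, a significant paired test among CAT participants answers the stated question about effectiveness whatever the controls did. The choice among the listed tests is left open in a section updated after data collection. What is at stake is the trial's main conclusion.

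**Working it through.** **1. The plan's own power figures.** The same section gives 92% and 99% power at 10 and 15 per group for care and responsibility, and 79% and 93% for walking. It states no effect size, SD, alpha or test, so direct reproduction is not possible. As a consistency check, I solved for the standardised effect at n = 10 and predicted power at n = 15, assuming two-sided alpha 0.05.

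- Two-sample t-test: d = 1.59 gives 98.8% for care; d = 1.31 gives 93.3% for walking.
- Paired t-test: d = 1.20 gives 99% for care; d = 0.98 gives 94% for walking.

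Both tests reproduce the stated figures to within 2 points. The power statement is therefore internally consistent, but it does not show whether a between-arm or a within-arm contrast was powered.

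**2. False significance under shared drift.**

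Inputs from the documents: 25 dyads per arm (Participants); three visits, with control visits matched in time (Study Groups).

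Assumed: alpha 0.05, normally distributed changes, no CAT effect, and the same mean drift of k SDs of change in both arms. No value of k is given in the documents.

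For the CAT-arm paired t-test, the noncentrality is k√n, on n − 1 = 24 degrees of freedom:

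| k (SD of change) | k√25 | CAT-arm paired t significant | Between-arm t on change significant |
|---|---|---|---|
| 0 | 0 | 5% | 5% |
| 0.2 | 1.0 | 16% | 5% |
| 0.3 | 1.5 | 30% | 5% |
| 0.5 | 2.5 | 67% | 5% |

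The last column follows because the drift cancels: the expected difference in mean change is k − k = 0. Simulation with 40,000 replicates gave 4.9% to 5.1%. At 24 per arm, close to the stated 97% retention, the paired-test figures for k = 0.2, 0.3 and 0.5 are 15%, 29% and 65%.

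On units: SD of change = SD of score × √(2(1 − r)), where r is the correlation between baseline and follow-up. At r = 0.5 the two SDs are equal.

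**3. What the form of baseline adjustment is worth.** Relative to comparing follow-up scores alone, the variance of the arm difference is 2(1 − r) for change scores and 1 − r² for ANCOVA. Their ratio is (1 − r²) / (2(1 − r)) = (1 + r)/2.

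| r (assumed) | Change score | ANCOVA | Ratio | Reduction |
|---|---|---|---|---|
| 0.3 | 1.40 | 0.91 | 0.65 | 35% |
| 0.5 | 1.00 | 0.75 | 0.75 | 25% |
| 0.7 | 0.60 | 0.51 | 0.85 | 15% |

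This matters only if the arms would otherwise be compared on simple change scores.

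**The case against.** The best reply is that the control comparison is plainly intended. Independent t-tests are in the list. The statistical section speaks of the CAT-control difference after accounting for baseline. The main Aim 2 and Aim 3 hypotheses name the controls, and Aim 3 Assessments item 1 brings the attachment test itself into a between-arm comparison at 6 weeks and 1 year. Regression with covariates is also listed, and that is compatible with ANCOVA. All of this stands, and it rules out several stronger readings that a reader might infer:

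- *Efficacy is judged mainly by before-after tests.* The plan does not rank its tests.
- *Controls are consulted only where CAT improved, which selects favourable outcomes.* The other planned control comparisons contradict this. Comparing CAT improvement with control change is also a valid between-arm contrast. In the simulation, a between-arm test run only after a significant CAT improvement favoured CAT in at most about 2.5% of null trials, which is no inflation.
- *The plan commits to t-tests on change scores.* It does not; the form of the model is left open.
- *Season distorts the 1-year result.* That visit falls at about the same time of year as baseline.
- *Paired tests lose many dyads.* Stated retention is 97%.

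The reply does not supply a rule. Nowhere is the between-arm result said to decide efficacy, and no baseline-adjusted model is specified. The sociability and secure-attachment prediction can still be met by change from baseline alone.

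**Conclusion.** The concern holds in this form: between-arm comparisons are planned but none is decisive, and within-arm tests are admitted as evidence of effectiveness. Under assumed shared drifts of 0.2 to 0.5 SD of change, the chance of a falsely significant CAT-arm result is about 16% to 67%, against 5% for the randomised contrast. These percentages are illustrations. They depend on the assumed drift, alpha 0.05 and normal changes, and they do not show that drift occurred. The direction of the problem does not depend on those assumptions: any drift towards improvement that both arms share raises the paired test's error and leaves the between-arm test's error unchanged.

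**What to change.** For every Aim 2 and Aim 3 efficacy outcome, state that the conclusion rests on the CAT-versus-control contrast at 6 weeks and 1 year.

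- **Scores:** use ANCOVA at each visit (follow-up score on arm and baseline score), or a mixed model with arm, visit, arm by visit and baseline score.
- **Secure attachment:** use logistic regression on arm and baseline classification where counts allow. Where they do not, the Fisher's exact test already listed can compare the arms, reported as unadjusted.
- **Population:** all randomised dyads, analysed as randomised.
- **Within-arm change:** report as descriptive only.
- **Aim 3 wording:** add the controls as comparator in the behavioural prediction.
- **Labelling:** say that the choice was made after data collection.

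The cost is SAP wording and the loss of within-arm p-values as headline results. The data required are those the three assessments already provide.
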